## 12.0 Data Management

- Analysis: The primary analysis will be a repeated measures ANOVA for each outcome. The primary independent variables are group (treatment vs. control), evaluation time (baseline and 1-4 weeks of using the device for the primary analysis; follow-up will be included in subsequent analysis), and their interaction. We will also include sex as an independent variable along with its interactions.

- Sample size justification: For the repeated measures design with a significance level of 0.0125 (adjusted for multiple comparisons), at least 80% power, and 5 primary time points, using a standard deviation of 6.4 s and compound symmetry correlation of 0.92 (observed in the pilot study), a sample size of 17 per group will be adequate to detect a minimum difference (futility level) of 7 s. Adjusting for 15% attrition, 20 per group is planned.
- Confidentiality: All data except for the consent forms and HIPPA forms will be de-identified at the time of data recording. All electronic data will be stored in a password-protected research server that is accessible to study personnel only. The server is backed up every day and maintained 24/7 by IT specialists. All paper data with personally identifiable information including the consent forms and HIPPA forms will be stored in a key-locked cabinet in a key-locked room that is accessible to study personnel only. Other paper data without personally identifiable information including testing sheets documenting testing sequences and notes will also be stored in a cabinet in a key-locked room that is accessible to study personnel only.
- Data sharing: Only de-identified coded data will be reported and/or shared with the public and other investigators in publications, in ClinicalTrials.gov, or via network storage.

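### The only stated significance level, 0.0125, reads as a flat Bonferroni split; Holm's step-down holds the same family-wise 0.05, is never less powerful, and gains from about 0 to 12 points of power per test

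*Combined protocol and SAP*

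**What the plan says.** Everything relevant is in section 12.0 (Data Management) of the combined protocol and SAP.

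- The Analysis paragraph states: "The primary analysis will be a repeated measures ANOVA for each outcome". The factors are group, evaluation time and their interaction, with sex added. The primary times are "baseline and 1-4 weeks of using the device for the primary analysis". The paragraph gives no significance level and no multiplicity rule.
- The sample size paragraph assumes a "significance level of 0.0125 (adjusted for multiple comparisons", with "at least 80% power, and 5 primary time points". Its variability figures are earlier data from the same group's work: "using a standard deviation of 6.4 s and compound symmetry correlation of 0.92 (observed in the pilot study". It concludes that "a sample size of 17 per group will be adequate" and calls this "adequate to detect a minimum difference (futility level) of 7 s". It then adds: "Adjusting for 15% attrition, 20 per group is planned".

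Neither paragraph gives the division 0.05/4, says what the four comparisons are, or names Bonferroni, Holm or any other procedure for the final p-values.

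**The concern.** Since 4 × 0.0125 = 0.05, the natural reading is that each of four comparisons will be judged at 0.0125 whatever the others show. That is valid but stricter than it needs to be. Once the smallest p-value has passed 0.0125, at most three null hypotheses can still be true, and holding the rest to 0.0125 gives up power without improving error control.

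The loss is greatest when several effects are real together. Sections 1.0 and 2.0 expect something of that kind: better sensory feedback leads to more hand use, then to neural plasticity and recovery of hand function. With 17 evaluable participants per group, power that can be had without recruiting anyone is worth taking.

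**Working it through.** **Inputs from section 12.0.** Level 0.0125, SD 6.4 s, compound symmetry correlation 0.92, 5 time points, difference 7 s, 17 per group, 15% attrition. **Assumed, because not stated:** two-sided tests, a family of four, family-wise level 0.05.

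**1. The plan's own sample size.** For the group difference in the mean of the 5 visits:

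- Effective SD = 6.4 × √((1 + 4 × 0.92)/5) = 6.4 × √0.936 = 6.19 s.
- By the normal approximation, n = 2 × (6.19/7)² × (2.498 + 0.842)² = 17.4, so 18 per group. Power at 17 is 78.8%. This agrees with the plan's 17 to within one participant.
- By noncentral t with 2 × 17 − 2 = 32 degrees of freedom, the noncentrality is 7/(6.19 × √(2/17)) = 3.30 and power at 0.0125 is 73.8%. This is the base used below, since t is the closer match at this size. The stated 80% is used as a second base.
- 17/(1 − 0.15) = 20, as planned.

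**2. Why Holm cannot do worse.** The ordered p-values are compared with 0.05/4 = 0.0125, 0.05/3 = 0.0167, 0.05/2 = 0.025 and 0.05, stopping at the first failure.

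- *Power.* No threshold is below 0.0125. If a p-value is at or below 0.0125, so are all smaller ones, and the procedure cannot stop before reaching it. Holm therefore rejects everything the flat rule rejects.
- *Error control.* With m true nulls, the first true null to be rejected is met when at least m hypotheses remain, so its p-value is at most 0.05/m. The chance that any of m true nulls has so small a p-value is at most m × 0.05/m = 0.05, whatever the dependence.

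**3. Size of the gain.** 200,000 simulated trials per scenario, four two-sided t-tests on 32 degrees of freedom, equal correlation between tests, every real effect at full design size. Gain in power per test, Holm minus flat 0.0125:

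| Real effects out of 4 | Base power | Gain in points, correlation 0 to 0.92 |
|---|---|---|
| 1 | 73.8% | 0.1 to 0.0 |
| 2 | 73.8% | 2.8 to 2.1 |
| 3 | 73.8% | 6.4 to 4.5 |
| 4 | 73.8% | 11.6 to 7.3 |
| 4 | 80% | 10.3 to 6.4 |

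With four real effects and the 73.8% base, power per test rises to 85.4%, 84.0% and 82.8% at correlation 0, 0.3 and 0.6. With a single real effect the threshold relaxes only after a true null has been falsely rejected, so there is almost nothing to gain. Family-wise error under Holm was 0.049 with all four nulls true and independent tests, and 0.037 to 0.043 with two true nulls. The entries at correlation 0.92 are approximate: if the variance estimates are also allowed to correlate, the four-effect gain from the 73.8% base is nearer 6 than 7 points.

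**4. Where there is nothing to gain.** For change from baseline, SD = 6.4 × √(2 × (1 − 0.92)) = 2.56 s and the noncentrality is 7/(2.56 × √(2/17)) = 7.97, so power at 0.0125 is already close to 100%. The group-by-time interaction with the same inputs has power above 99.9% for each of three time profiles tried. No threshold above 0.0125 can add anything useful there.

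**The case against.** The strongest reply is that the plan contains no flat rule to correct. The level 0.0125 occurs only as a sample-size input, and sizing at 0.05/4 suits Holm as well as Bonferroni because it is Holm's first step. The Analysis paragraph is silent, so the final analysis could be Holm already. This stands in part: a reader might infer that the plan commits itself to holding all four comparisons to 0.0125, and the text does not say so. But silence leaves the flat split as the natural reading and the choice open after the data are seen. Writing the rule down resolves both.

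A reader might also infer that Holm would add some 9 to 12 points to every test. The documents do not support that. This range needs four real effects, all of full design size, a 73.8% base and correlation no higher than 0.6. The SD and difference in section 12.0 are in seconds and so describe a timed outcome; nothing is given for the others. Under section 10.0, EEG, grip control and accelerometry are measured only at baseline, post and follow-up. Under section 5.0, participants with TMS contraindications stay in the trial without that test, so the plasticity comparison may have fewer than 17 per group. Four equally powered comparisons are therefore an assumption.

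Nor does the gain carry over regardless of what the four comparisons are. If they are the four post-baseline times, it is about 6 to 7 points for raw values at correlation 0.92, with all four effects real, and essentially none for change from baseline.

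Finally, Bonferroni is valid, and section 13.0 calls this a single-site pilot. True, but that does not make the flat rule preferable to one that rejects everything it rejects at the same error rate.

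**Conclusion.** The point holds as a conditional one. If every comparison is held to 0.0125, Holm's procedure is the better choice: same family-wise 0.05, same sample size, never less power. Per test, from the 73.8% base, it gains about 0 points with one real effect, 2 to 3 with two, 4.5 to 6.5 with three and 7 to 12 with four; from the stated 80%, four real effects gain 6 to 10.

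These figures rest on a family of four at family-wise 0.05, two-sided tests, equal full-size effects and correlation between 0 and 0.92. They do not apply to a test already near 100% power, such as change from baseline or group-by-time with the plan's correlation. This is a gain in efficiency and clarity; a flat 0.0125 would not inflate the type I error over four comparisons.

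**What to change.** In the Analysis paragraph of section 12.0, name the four primary comparisons (outcome, model term and time) and add, before unblinding: *The four primary comparisons are tested by Holm's procedure at a family-wise level of 0.05; the ordered p-values are compared with 0.0125, 0.0167, 0.025 and 0.05, stopping at the first that fails.* Naming the family comes first, because the rule cannot be applied without it. Keep 0.0125 in the sample size calculation, described as the first-step level; 17 evaluable and 20 planned per group do not change.

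The cost is a few words and no participants. The small downside is that simultaneous confidence intervals matching Holm's decisions are less simple than Bonferroni intervals. Ordinary 95% intervals can still be reported, labelled as unadjusted.

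### The 17 per group stated to give at least 80% power for 7 s does not match any test in the planned repeated measures ANOVA; the contrast and its power need restating

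*Combined protocol and SAP*

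**What the plan says.** Everything relevant is in section 12.0 Data Management of the combined protocol and SAP.

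- Analysis: "The primary analysis will be a repeated measures ANOVA for each outcome". The independent variables are group, time and their interaction, with sex and its interactions added. Time in the primary analysis is defined as "evaluation time (baseline and 1-4 weeks of using the device for the primary analysis", which makes five time points.
- Sample size: the calculation is made "with a significance level of 0.0125 (adjusted for multiple comparisons), at least 80% power, and 5 primary time points", with a standard deviation of 6.4 s and a compound symmetry correlation of 0.92 from the pilot study. It concludes that "a sample size of 17 per group will be adequate to detect a minimum difference (futility level) of 7 s".
- Attrition: "Adjusting for 15% attrition, 20 per group is planned". Section 6.0 gives the same total of 40.

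The paragraph does not say which ANOVA term the 7 s refers to, whether the 0.0125 is one- or two-sided, or which power method was used.

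**The concern.** A sample size statement should describe the test that will be run. The ANOVA offers two tests that compare the groups: the group main effect and the group-by-time interaction. The listed inputs are those of the usual formula for a time-averaged group difference, that is, the main effect. An ANOVA F-test of that effect is non-directional and uses an estimated error variance with about 32 degrees of freedom, so it needs somewhat more patients than a normal approximation or a one-sided test.

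The 80% figure is the trial's justification for its size. If inference rests on the group main effect, a non-significant result would be read against a power that this test does not have. The five-time average also includes baseline, where randomised groups cannot yet differ because of treatment, so it dilutes any effect that develops later.

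**Working it through.** **Inputs (section 12.0).** SD 6.4 s; compound symmetry correlation 0.92; 5 times; alpha 0.0125; power 80%; difference 7 s; 17 evaluable per group. Sidedness is not stated. Two-sided is taken as the main case because the planned test is an F-test.

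**1. The plan's own figure.** Variance factor for the mean of five measurements: (1 + 4 × 0.92)/5 = 0.936. SD of a patient's mean: 6.4 × √0.936 = 6.192 s.

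Normal formula, two-sided: n = 2 × (2.498 + 0.842)² × 6.192² / 7² = 17.45 per group, which rounds up to 18. Power at 17 is 78.8%.

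Attrition: 17/0.85 = 20, which agrees with the plan.

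**2. The ANOVA F-test of the group main effect.** In a balanced design this is the F-test on patient means, with 1 and 2n − 2 degrees of freedom and noncentrality 7² / (6.192² × 2/n). At n = 17 the noncentrality is 10.86 and the critical value is 7.01.

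| Evaluable per group | Power for 7 s |
|---|---|
| 17 | 73.8% |
| 18 | 76.9% |
| 19 | 79.8% |
| 20 | 82.4% |

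With sex and its interaction with group in the model (30 error degrees of freedom), power at 17 is 73.4%. The difference detectable with 80% power at 17 per group is 7.46 s.

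**3. Can another reading give 17?**

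- One-sided 0.0125 t-test of the same average: 79.4% at 16 and 82.2% at 17, so 17 is the smallest adequate size.
- Rounding of the inputs, all in the favourable direction (SD 6.35, correlation 0.915, 7.05 s): the normal formula gives 16.9 per group and 80.4% power at 17, but the F-test gives 75.5%.
- Single time point (SD 6.4), two-sided: the normal formula gives 18.64, so 19; the F-test at 17 has 70.4% power.
- Group-by-time F-test: noncentrality (n/2) × Σ(δ − mean δ)² / [6.4² × (1 − 0.92)], with 4 and 4(2n − 2) degrees of freedom. For a 7 s difference emerging after baseline as a step, as a linear rise or at week 4 only, the noncentrality at 17 per group is 101.7, 79.4 and 101.7. Power exceeds 99.9% in each case, and 4 to 5 per group already reach 80%. So 17 cannot have come from this test.

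**4. What averaging in baseline costs.** A 7 s effect at weeks 1 to 4 with none at baseline averages to 4 × 7/5 = 5.6 s, for which the main-effect F-test at 17 per group has 50% power. A linear rise to 7 s at week 4 averages to (0 + 1.75 + 3.5 + 5.25 + 7)/5 = 3.5 s, with 18% power.

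**5. A baseline-adjusted comparison of weeks 1 to 4.** Variance factor: (1 + 3 × 0.92)/4 − 0.92² = 0.940 − 0.8464 = 0.0936. SD: 6.4 × √0.0936 = 1.958 s. With 17 per group and two-sided 0.0125, the F-test has 80% power for 2.36 s.

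**The case against.** The strongest reply is that section 12.0 names neither the contrast nor the sidedness, so 73.8% is the power of one reading of the plan. The interaction is the ANOVA term closest to the question of differential change from baseline, and its power is ample. The stated size also reproduces closely: the normal formula misses 80% by only 1.2 points, rounding in the pilot inputs can close that gap, and a one-sided t-test gives exactly 17. If all 40 patients are evaluable, even the main-effect F-test has 82.4% power. Section 13.0 calls the study a pilot trial, and the SD and correlation are themselves pilot estimates.

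Much of this stands. A reader might infer that the trial is underpowered, or that a null result would be uninformative. The documents do not support either for the interaction or for a baseline-adjusted comparison. A reader might also infer that 17.45 was simply rounded down; the plan does not show how 17 was obtained.

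What does not stand is that the paragraph can be left as it is. Favourable rounding rescues only the normal approximation. The one-sided test is not the planned one. The interaction needs 4 to 5 per group, so it does not explain 17. On each reading, the stated size and the planned test have to be brought into line.

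**Conclusion.** The concern holds as a mismatch between the sample size statement and the planned analysis. No test in the planned ANOVA makes 17 per group the size for 80% power at 7 s. For the two-sided group main effect over five times, the shortfall at 17 is about 6 power points by the F-test (73.8% against 80%), or about 0.5 s in detectable difference (7.46 s against 7 s), or 3 evaluable patients per group (20 against 17).

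These figures assume the plan's SD, compound symmetry at 0.92, a two-sided 0.0125 level and the full 15% loss. They apply to the group main effect only. The flat statement that the trial's power is wrong goes too far, because the plan does not say that this effect is the primary contrast and the group-by-time test has over 99.9% power.

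**What to change.** Keep 40 patients and rewrite the sample size paragraph.

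- Preferred: name as the primary contrast the baseline-adjusted group comparison over weeks 1 to 4, two-sided at 0.0125, and state power for it. Under the plan's correlation of 0.92, 17 evaluable per group detect about 2.4 s with 80% power. Make the analysis paragraph name the same contrast.
- If the five-time group main effect is kept: state about 74% power for 7 s, or 80% power for about 7.5 s, at 17 evaluable per group, and say that the average includes baseline.
- If a one-sided test was intended: say so, and align the planned test with it, since the ANOVA F-test is not directional.

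In each case, state the power method. The cost is one rewritten paragraph, a matching line in the analysis text and, only if the main effect is kept, a slightly less favourable stated power. The preferred option leans on the pilot correlation of 0.92, so its detectable difference should be presented as conditional on that value.

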## 13.0 Provisions to Monitor the Data to Ensure the Safety of Subjects

The proposed research is a single site pilot clinical trial that is concerned with an intervention using an investigational device in a double-blinded randomized controlled design. A Data Safety Monitoring Board (DSMB) will be used.

- A DSMB will ensure the safety of participants and the validity and integrity of data collected during the tenure of the project. The overall framework involves review of the enrollment/retention and safety and adverse event data by the DSMB during the proposed research.
- DSMB composition: The DSMB will be composed of three professionals with expertise related to the proposed area of study who are not involved with the study design or experiments. Specifically, the DSMB will include: (1) a board-certified stroke neurologist who also is a stroke recovery researcher and is experienced in care of chronic stroke survivors and their recovery; (2) a registered and licensed occupational therapist who also is a quantitative researcher in outcomes measurement and research design; and (3) a biostatistician with expertise in design and analysis of clinical trials. This multidisciplinary group has experience with management and monitoring of clinical intervention trials involving individuals following stroke, and brings substantial expertise adequate to serve as the DSMB.
- DSMB responsibilities: The responsibilities of the DSMB are as follows.
  - Prior to any enrollment, the DSMB will review the study design, protocol, informed consent documents, amendments, recruitment/enrollment plan, statistical analysis plan, and data and safety monitoring plan, and document the agreement or recommendation.

- Once the enrollment begins, the DSMB will convene every 6 months to review the progress of the trial.
- The DSMB will review the enrollment/retention data including new enrollments, progression of the enrollees' participation in the study, any discontinuation of participation in the study with or without adverse events, and the current enrollment status compared to the project time line.
- The DSMB will review data quality and quality control data.
- The DSMB will review safety and adverse event data. The DSMB will review the aggregated summary data as well as the individual participants' data (de-identified). The DSMB will discuss participant risk vs. benefit and other factors that may potentially affect study outcomes. The DSMB will make recommendations for appropriate action to maintain a reasonable safety profile for the study.
- The DSMB will ensure that all serious adverse events have been followed to resolution, and that the appropriate agencies (including the IRB and/or federal funding agency) have been informed.
- The DSMB will advise the IRB and the study investigators as to whether the protocol should continue as scheduled or undergo any modification due to findings from the monitoring process. The DSMB may recommend stopping the study early if the study has unanticipated safety concerns that warrant stopping.
- The DSMB will review study performance as well as make recommendations and assist in resolution of problems reported by the PI.
- The DSMB will ensure the confidentiality of the study data and the results of monitoring.
- The DSMB will document their reviews in writing and provide a report to the IRB to summarize oversight activities, recommendations and any concerns regarding participant safety. The report will include participant characteristics (including distributions across race and sex), retention and disposition of study participants, quality assurance issues and reports of adverse events, significant/unexpected adverse events and serious adverse events.
- The DSMB will review final analysis results upon completion of the data collection.

• Reporting of safety data: All serious adverse events will be reported to the IRB as they occur. All enrollment/retention data, and safety and adverse event data will be reported to the DSMB during the review. The DSMB will review the data and submit a report to the IRB. Summative safety data will be reported to ClinicalTrials.gov, and in publications. As such, we will register this study in ClinicalTrials.gov as soon as the study commences and report results including all adverse events as soon as the study is completed following the guidelines. To protect participants' confidentiality, personally identifiable information will not be used for reporting. Only de-identified or aggregated data will be used for reporting.

## 14.0 Withdrawal of Subjects (if applicable)

- Subjects who do not show up on scheduled visits may be withdrawn by the investigator.
- For those who voluntarily withdraw from the research, their data collected up to that point may be used by the investigator.

## 15.0 Risks to Subjects

- There is a slight risk for loss of confidentiality although researchers will take appropriate steps to protect any information collected about the participants. There is a minor risk of physical and mental fatigue from engaging in the study activity. There is a minor risk of skin irritation from wearing the wristband. There is a minor risk of discomfort in moving the arm/hand while wearing a device on the wrist, although the TheraBracelet device weighs only 40 g.
- EEG: There is a minor risk of discomfort in wearing a head cap attached with a bundle of wires. Also, the gel used for the electrodes will get hair messy.
- TMS/electrical nerve stimulation: There is a serious risk that TMS could move iron-containing objects in or around the face or head, which in the process could possibly harm the person. There is a slight risk of a seizure with TMS; the incidence of seizures is very low and mostly associated with high frequency repetitive TMS (rTMS) which will not be used in this study. Instead we will use single-pulse TMS, which is much safer. There is a minor risk of scalp discomfort and headache. A TMS stimulus may feel like a slight tap to the skull. There may be discomfort from the muscle contraction that occurs in the hand muscle in response to the TMS. There is a very low risk of hearing loss due to the clicking sounds that the TMS machine makes. Safety of TMS in pregnancy is unknown. The electrical nerve stimulation will produce sensation on the wrist, which may cause discomfort. The use of tape or other adhesives to secure electrodes for EMG measurement and/or for electrical nerve stimulation during testing may cause some mild skin irritation. Subjects with contraindications (e.g., epilepsy, concussion, metal in the head/neck, pregnancy) will not be tested for TMS. Subjects will be screened for safety before administering TMS (e.g., removal of all loose metal objects like earrings or nose rings).
- MRI: There is a serious risk that MRI could move iron-containing objects in the MRI room, which could in the process possibly harm the person. The 3T MRI scanner is unsafe for pregnancy. There is discomfort by claustrophobia and by the loud banging noise. Temporary hearing loss has been reported from the loud noise from the MRI machine. The person may also feel uncomfortable as s/he will be asked not to swallow for a while. Subjects with contraindications (e.g., metal in the body such as a fragment in the eye, aneurysm clips, ear implants, spinal nerve stimulators, a pacemaker, or an implant electrical device, claustrophobia, pregnancy) will not be tested for MRI. Subjects will be screened for safety before entering the MRI room (e.g., removal of all loose metal objects like earrings or nose rings).
- There is a minor risk that subjects feel discomfort from wearing the accelerometer devices on their wrists for all day.
- Potential risks that might be associated with use of wrist vibration for a prolonged time include wrist skin irritation, increased upper limb pain, increased spasticity, weakness, and worsening of hand sensation or dexterity. These risks are expected to be rare because the intensity of vibration used in TheraBracelet is subliminal while we are exposed to higher-intensity, suprathreshold vibration daily (e.g. from a phone, car). Currently there is no vibration exposure guideline for this small level of vibration, as the

U.S. Occupational Safety and Health Administration provides vibration exposure guidelines only for high-intensity vibration such as jackhammers and hand-held powered drills. Currently there are no known side effects using this small imperceptible (unfelt) level of vibration used in the proposed study. TheraBracelet has been used for at least 8 hours daily for a month in chronic stroke survivors without safety concern in our pilot study. Nonetheless, safety of using TheraBracelet will be systematically monitored. Potential risk also includes discomfort of wearing a device on the wrist everyday.

